9.7.4. Laboratory Results

Analysis of laboratory data will be descriptive and conducted on the safety population. Summary of laboratory data (including thiamine levels) and change from baseline will also be performed by subject and by cycle. For each of the parameters, a baseline value is defined as the last value or measurement taken up to the first dose of fedratinib.

Hematological toxicities will be assessed from laboratory parameters. Worst NCI CTCAE grades of leukopenia, neutropenia, thrombocytopenia, and anemia will be calculated according to the NCI common terminology criteria.

Qualitative and quantitative results will be summarized for hematological toxicities. Qualitative data (worst NCI CTCAE grade) will be summarized by cycle and by subject.

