4.2. Inclusion Criteria

Subjects must satisfy the following criteria to be enrolled in the study:

1. Subject is at least 18 years of age at the time of signing the informed consent form (ICF)
2. Subject has an Eastern Cooperative Oncology Group (ECOG) ([Appendix J](#)) Performance Score (PS) of 0, 1 or 2
3. Subject has diagnosis of primary myelofibrosis (PMF) according to the 2016 World Health Organization (WHO) criteria ([Appendix G](#), [Appendix H](#)), or diagnosis of post-ET or post-PV myelofibrosis according to the IWG-MRT 2007 criteria ([Appendix I](#)), confirmed by the most recent local pathology report
4. Subject has a DIPSS Risk score of Intermediate or High ([Appendix F](#))
5. Subject has a measurable splenomegaly during the screening period as demonstrated by spleen volume of $\geq 450 \text{ cm}^3$ by MRI or CT-scan assessment or by palpable spleen measuring $\geq 5 \text{ cm}$ below the left costal margin
6. Subject has been previously exposed to ruxolitinib while diagnosed with MF (PMF, post-ET MF or post-PV MF), and must meet at least one of the following criteria (a or b)
 - a. Treatment with ruxolitinib for ≥ 3 months
 - b. Treatment with ruxolitinib for ≥ 28 days complicated by any of the following:
 - Development of a red blood cell transfusion requirement (at least 2 units/month for 2 months) or
 - Grade ≥ 3 AEs of thrombocytopenia, anemia, hematoma, and/or hemorrhage while on treatment with ruxolitinib
7. Subject must have treatment-related toxicities from prior therapy resolved to Grade 1 or pretreatment baseline before start of last therapy prior to fedratinib treatment.
8. Subject must understand and voluntarily sign an ICF prior to any study-related assessments/procedures being conducted
9. Subject is willing and able to adhere to the study visit schedule and other protocol requirements
10. A female of childbearing potential (FCBP) must:
 - a. Have two negative pregnancy tests as verified by the Investigator prior to starting study therapy. She must agree to ongoing pregnancy testing during the course of the study, and after end of study therapy. This applies even if the subject practices true abstinence* from heterosexual contact.

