4.3. Exclusion Criteria

The presence of any of the following will exclude a subject from enrollment:

1. Any of the following laboratory abnormalities:
 - a. Platelets < 50,000/ μ L
 - b. Absolute neutrophil count (ANC) < 1.0 x 10⁹/L
 - c. White blood count (WBC) > 100 x 10⁹/L
 - d. Myeloblasts > 5 % in peripheral blood
 - e. Estimated glomerular filtration rate < 30 mL/min/1.73 m² (as per the Modification of Diet in Renal Disease [MDRD] formula) ([Appendix K](#))
 - f. Serum amylase or lipase > 1.5 x ULN (upper limit of normal)
 - g. Aspartate aminotransferase (AST) or alanine aminotransferase (ALT) > 3 x ULN
 - h. Total bilirubin > 1.5 x ULN, subject's total bilirubin between 1.5 – 3.0 x ULN are eligible if the direct bilirubin fraction is < 25% of the total bilirubin
2. Subject is pregnant or lactating female
3. Subject with previous splenectomy
4. Subject with previous or planned hematopoietic cell transplant
5. Subject with prior history of encephalopathy, including Wernicke's

6. Subject with signs or symptoms of encephalopathy including Wernicke's (eg, severe ataxia, ocular paralysis or cerebellar signs)
7. Subject with thiamine deficiency, defined as thiamine levels in whole blood below normal range according to institutional standard and not corrected prior to enrollment on the study
8. Subject with concomitant treatment with or use of pharmaceutical, herbal agents or food known to be strong or moderate inducers of Cytochrome P450 3A4 (CYP3A4), or dual CYP2C19 and CYP3A4 inhibitors (refer to Section 8 and [Appendix L](#))
9. Subject on any chemotherapy, immunomodulatory drug therapy (eg, thalidomide, interferon-alpha), anagrelide, immunosuppressive therapy, systemic corticosteroids > 10 mg/day prednisone or equivalent. Subjects who have had prior exposure to hydroxyurea (eg, Hydrea) in the past may be enrolled into the study as long as it has not been administered within 14 days prior to the start of fedratinib treatment
10. Subject has received ruxolitinib within 14 days prior to the start of fedratinib
11. Subject on treatment with myeloid growth factor (eg, granulocyte-colony stimulating factor [G-CSF]) within 14 days prior to the start of fedratinib treatment
12. Subject with previous exposure to Janus kinase (JAK) inhibitor(s) for more than 1 cycle other than ruxolitinib treatment
13. Subject on treatment with aspirin with doses > 150 mg daily
14. Subject with major surgery within 28 days before starting fedratinib treatment

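### Laboratory hematological toxicity is tabulated as worst CTCAE grade with no reference to baseline grade, so unchanged anemia present at entry can appear as Grade 3-4 toxicity in those tables

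*Combined protocol and SAP*

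**What the plan says.** Section 9.7.4 (Laboratory Results) assesses hematological toxicity from laboratory parameters. The rule is: "Worst NCI CTCAE grades of leukopenia, neutropenia, thrombocytopenia, and anemia will be calculated according to the NCI common terminology criteria". The presentation is: "Qualitative data (worst NCI CTCAE grade) will be summarized by cycle and by subject". The section defines a baseline value, but the only use it states for it is: "Summary of laboratory data (including thiamine levels) and change from baseline will also be performed by subject and by cycle".

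Four other places bear on what subjects bring with them at entry:

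- Section 1.1.1 lists moderate-to-severe anemia among the usual presenting features of the disease.
- Section 4.3, exclusion 1, rules out subjects with "Platelets < 50,000" per microliter and those with an ANC below 1.0 x 10⁹/L. Items a to h include no hemoglobin limit.
- Section 4.2, criterion 6, can be met by at least 3 months of ruxolitinib (6a). It can also be met by at least 28 days complicated by one of two events (6b). The first event is "Development of a red blood cell transfusion requirement (at least 2 units/month for 2 months) or"; the second is Grade 3 or higher "AEs of thrombocytopenia, anemia, hematoma, and/or hemorrhage while on treatment with ruxolitinib".
- Section 4.2, criterion 7: "Subject must have treatment-related toxicities from prior therapy resolved to Grade 1 or pretreatment baseline before start of last therapy prior to fedratinib treatment".

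Two neighboring analyses do use baseline. In Section 9.7.2 a treatment-emergent adverse event must start, or rise in grade, after the first dose. In Section 9.7.6 vital-sign abnormalities are summarized by baseline status, and every criterion in Table 5 includes a change from baseline.

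**The concern.** A worst-grade table without the baseline grade cannot tell a low hemoglobin that was there before the first dose from one that arose on fedratinib. Change from baseline in values does not fill the gap, because a mean change in hemoglobin does not say how many of the Grade 3 subjects entered at Grade 3.

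The trial has one arm, so baseline is its only internal reference. Without it, the laboratory anemia rate mixes disease with drug and cannot be reconciled with the adverse event rate from the same trial. There is also an external comparison to spoil. Section 1.2 reports 38.1% Grade 3 or 4 anemia among the treatment-emergent results of the earlier single-arm study in ruxolitinib-treated patients. A reader may set this trial's laboratory rate beside that figure, although the two would be different quantities.

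**Working it through.** The documents state no figure on this point, so there is none to reproduce. The check has two parts.

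**1. Can Grade 3 anemia be present at entry?**

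- No exclusion removes it: exclusion 1 limits platelets, neutrophils, white cells and blasts, but not hemoglobin.
- Criterion 7 covers only toxicity caused by prior treatment, so anemia due to the disease is outside it. Even for treatment toxicity it accepts return to a pretreatment level that may itself be abnormal.
- Appendix F gives hemoglobin below 10 g/dL two DIPSS points. Two points alone make intermediate-1, which satisfies inclusion criterion 4. Anemia thus helps a subject qualify, although the documents do not tie that cut-off to a CTCAE grade.

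So it can be present. How often is not stated.

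**2. What does the stated rule do with it?**

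Inputs, all but the first assumed:

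- N = 110 subjects (Section 9.3).
- b = share at Grade 3 or higher anemia at baseline; taken as 5%, 10% and 20%.
- e = share of the rest who newly reach Grade 3-4; taken as 30%.
- Subjects already at Grade 3 or higher have at least one on-treatment value at that grade and do not worsen further.

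Formulas, both over all treated subjects:

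- Worst-grade rate W = b + (1 − b) × e
- Treatment-emergent rate E = (1 − b) × e
- Excess W − E = b, whatever the value of e

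| b | W | E | Excess | Subjects of 110 |
|---|---|---|---|---|
| 5% | 0.05 + 0.95 × 0.30 = 33.5% | 0.95 × 0.30 = 28.5% | 5 points | 5.5 |
| 10% | 0.10 + 0.90 × 0.30 = 37.0% | 0.90 × 0.30 = 27.0% | 10 points | 11 |
| 20% | 0.20 + 0.80 × 0.30 = 44.0% | 0.80 × 0.30 = 24.0% | 20 points | 22 |

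With e = 20% the pairs are 24.0% and 19.0%, 28.0% and 18.0%, and 36.0% and 16.0%; the excess is unchanged. With e = 0, no new cases at all, the table still shows b.

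The last assumption makes b an upper limit. If a share q of the baseline Grade 3 or higher subjects has an on-treatment value at that grade and a share w worsens further, the excess is b × (q − w), which cannot exceed b.

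The 30% in this illustration is a rate among subjects below Grade 3 at baseline. W and E are rates among all 110. Setting W against 30% would mix denominators and give gaps of 3.5, 7 and 14 points, which are not the excess.

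**The case against.** The strongest reply is that little depends on this table. Section 9.7.4 calls the laboratory analysis descriptive and attributes nothing to fedratinib; causality is judged event by event under Section 10.2.3. No decision rule, sample size or efficacy endpoint uses it. This stands, and it limits the weight of the point.

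Three stronger readings are tempting, and the documents do not support them.

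- A reader might infer that the secondary safety endpoint is inflated, since Table 2 mentions laboratory parameters. But Table 2 counts Grade 3-4 adverse events. Section 10.3 makes a laboratory abnormality an adverse event only if it leads to discontinuation, needs intervention or is judged clinically important. Section 9.7.2 then requires onset or worsening after the first dose. The endpoint is therefore largely protected.
- A reader might infer that criterion 6b selects subjects who need transfusion at entry. It is one of two alternative routes, it describes a complication during ruxolitinib, and criterion 7 may remove part of it. The case rests on disease-related anemia and the missing hemoglobin floor, not on 6b.
- A reader might infer that no planned table will separate baseline from emergent grades. Section 9.1 calls Section 9 an overview and leaves final methods to a SAP, and no separate SAP text is in the document supplied. Shift tables may be planned there. That would not correct the rule as Section 9.7.4 states it.

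It is also too strong to say that an unchanged subject is counted in every cycle, since transfusion may raise hemoglobin in some. The by-subject worst grade would still pick up any single value at that grade.

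**Conclusion.** The point holds for the laboratory grade tables in Section 9.7.4 and should be put right there. As written, the rule lets pre-existing, unchanged anemia be tabulated as hematological toxicity, while the plan's own rules for adverse events and vital signs take baseline into account. Low platelet or neutrophil grades above the entry floors would be counted in the same way.

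The bias can only be upward. Its size is at most the baseline prevalence of Grade 3 or higher anemia: 5 to 20 percentage points over the assumed range of 5% to 20%. That prevalence is not in the documents, so the range shows the mechanism and is not an estimate for this trial. Nothing here touches the primary endpoint.

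**What to change.** In Section 9.7.4 and the SAP:

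- Keep the worst-grade summary and state its window: first dose through 30 days after the last dose, matching Section 9.7.2.
- Add, for each hematology parameter, a shift table of baseline grade by worst on-treatment grade.
- Report as treatment-emergent laboratory toxicity only grades worse than baseline.
- Give the Grade 3-4 rate also among subjects below Grade 3 at baseline, with that denominator shown.

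If the SAP already plans this, align Section 9.7.4 with it.

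The cost is a few lines of text and one set of tables. Table 3 already schedules hematology at screening and on Day 1 of each cycle, so no new data or visits are needed. Because the worst-grade summary is kept, no planned display is lost.

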9.7.5. Electrocardiogram (ECG)

All ECG data will be provided in a listing.

9.7.6. Vital Signs

Vital signs will be summarized based on the number of subjects with at least one potentially clinically significant abnormality (PCSA) occurring during the observation period according to baseline status. The PCSA criteria are provided in [Table 5](#).

Table 5: PCSA Criteria for Vital Signs and Weight

Parameter	PCSA
Heart (bpm)	≤ 50 bpm and decrease from baseline ≥ 20 bpm ≥ 120 bpm and increase from baseline ≥ 20 bpm
SBP (mmHg)	≤ 95 mmHg and decrease from baseline ≥ 20 mmHg ≥ 160 mmHg and increase from baseline ≥ 20 mmHg
DBP (mmHg)	≤ 45 mmHg and decrease from baseline ≥ 10 mmHg ≥ 110 mmHg and increase from baseline ≥ 10 mmHg
Weight (kg)	≥ 5 % increase from baseline ≥ 5 % decrease from baseline

DBP = diastolic blood pressure; kg = kilograms; mmHg = millimeters of mercury; PCSA = potentially clinically significant abnormalities; SBP = systolic blood pressure.

9.9. Interim Analysis

A formal interim analysis is not planned in this study.

9.10. Steering Committee

The conduct of this trial will be overseen by a steering committee (SC), presided over by a coordinating Principal Investigator, and if possible, the representative Regional Investigators from countries participating in this study.

The SC will serve in an advisory capacity to the Sponsor. Operational details for the SC will be detailed in a separate SC charter.

10. ADVERSE EVENTS

10.1. Monitoring, Recording and Reporting of Adverse Events

An AE is any noxious, unintended, or untoward medical occurrence that may appear or worsen in a subject during the course of a study. It may be a new intercurrent illness, a worsening concomitant illness, an injury, or any concomitant impairment of the subject's health, including laboratory test values (as specified by the criteria in Section 10.3), regardless of etiology. Any worsening (ie, any clinically significant adverse change in the frequency or intensity of a pre-existing condition) should be considered an AE. A diagnosis or syndrome should be recorded on the AE page of the CRF rather than the individual signs or symptoms of the diagnosis or syndrome.

Abuse, withdrawal, sensitivity or toxicity to an investigational product should be reported as an AE. Overdose, accidental or intentional, whether or not it is associated with an AE should be reported on the overdose CRF. (See Section 7.2.4 for the definition of overdose.) Any sequela of an accidental or intentional overdose of an investigational product which meets the definition of an adverse event should be reported as an AE on the CRF. If the sequela of an overdose meets serious criteria, then it must be marked as serious on the CRF. The overdose itself should not be reported as an SAE.

Complete data about drug administration, including any overdose, regardless of whether the overdose was accidental or intentional, should be reported in the case report form.

In the event of overdose, the subject should be monitored as appropriate and should receive supportive measures as necessary. There is no known specific antidote for fedratinib overdose. Actual treatment should depend on the severity of the clinical situation and the judgment and experience of the treating physician.

All subjects will be monitored for AEs during the study. Assessments may include monitoring of any or all of the following parameters: the subject's clinical symptoms, laboratory, pathological, radiological or surgical findings, physical examination findings, or findings from other tests and/or procedures.

All AEs will be recorded by the Investigator from the time the subject signs informed consent until 30 days after the last dose of fedratinib, as well as those SAEs made known to the investigator at any time thereafter that are suspected of being related to fedratinib AE and SAEs. All adverse events (serious/non-serious) will be recorded on the CRF and in the subject's source documents. Refer to Section 10.5 for instructions on how to report SAEs to Drug Safety.

10.2. Evaluation of Adverse Events

A qualified Investigator will evaluate all adverse events as to:

10.2.1. Seriousness

An SAE is any AE occurring at any dose that:

- Results in death;

- Is life-threatening (ie, in the opinion of the Investigator, the subject is at immediate risk of death from the AE);
- Requires inpatient hospitalization or prolongation of existing hospitalization (hospitalization is defined as an inpatient admission, regardless of length of stay);
- Results in persistent or significant disability/incapacity (a substantial disruption of the subject's ability to conduct normal life functions);
- Is a congenital anomaly/birth defect;
- Constitutes an important medical event.

Important medical events are defined as those occurrences that may not be immediately life-threatening or result in death, hospitalization, or disability, but may jeopardize the subject or require medical or surgical intervention to prevent one of the other outcomes listed above. Medical and scientific judgment should be exercised in deciding whether such an AE should be considered serious.

Events **not considered** to be SAEs are hospitalizations for:

- a standard procedure for protocol therapy administration. However, hospitalization or prolonged hospitalization for a complication of therapy administration will be reported as an SAE.
- routine treatment or monitoring of the studied indication not associated with any deterioration in condition.
- the administration of blood or platelet transfusion as routine treatment of studied indication. However, hospitalization or prolonged hospitalization for a complication of such transfusion remains a reportable SAE.
- a procedure for protocol/disease-related investigations (eg, surgery, scans, endoscopy, sampling for laboratory tests, bone marrow sampling). However, hospitalization or prolonged hospitalization for a complication of such procedures remains a reportable SAE.
- hospitalization or prolongation of hospitalization for technical, practical, or social reasons, in absence of an AE.
- a procedure that is planned (ie, planned prior to start of treatment on study); must be documented in the source document and the CRF. Hospitalization or prolonged hospitalization for a complication remains a reportable SAE.
- an elective treatment of or an elective procedure for a pre-existing condition, unrelated to the studied indication, that has not worsened from baseline.
- emergency outpatient treatment or observation that does not result in admission, unless fulfilling other seriousness criteria above.

For each AE, the Investigator will provide information on severity, start and stop dates, relationship to the IP, action taken regarding the IP, and outcome.

10.2.2. Severity/Intensity

For each AE, the Investigator must assess the severity/ intensity of the event.

The severity/intensity of AEs will be graded based upon the subject's symptoms according to the current active minor version of the Common Terminology Criteria for Adverse Events (CTCAE Version 5.0);

https://ctep.cancer.gov/protocolDevelopment/electronic_applications/ctc.htm

AEs that are not defined in the CTCAE should be evaluated for severity/intensity according to the following scale:

- Grade 1 = Mild – transient or mild discomfort; no limitation in activity; no medical intervention/therapy required
- Grade 2 = Moderate – mild to moderate limitation in activity, some assistance may be needed; no or minimal medical intervention/therapy required
- Grade 3 = Severe – marked limitation in activity, some assistance usually required; medical intervention/therapy required, hospitalization is possible
- Grade 4 = Life-threatening – extreme limitation in activity, significant assistance required; significant medical intervention/therapy required, hospitalization or hospice care probable
- Grade 5 = Death - the event results in death

The term “severe” is often used to describe the intensity of a specific event (as in mild, moderate or severe myocardial infarction); the event itself, however, may be of relatively minor medical significance (such as severe headache). This criterion is *not* the same as “serious” which is based on subject/event *outcome* or *action* criteria associated with events that pose a threat to a subject’s life or functioning.

Seriousness, not severity, serves as a guide for defining regulatory obligations.

10.2.3. Causality

The Investigator must determine the relationship between the administration of fedratinib and the occurrence of an AE as Not Suspected or Suspected as defined below:

Not suspected: a causal relationship of the adverse event to fedratinib administration is **unlikely or remote**, or other medications, therapeutic interventions, or underlying conditions provide a sufficient explanation for the observed event.

Suspected: there is a **reasonable possibility** that the administration of fedratinib caused the adverse event. ‘Reasonable possibility’ means there is evidence to suggest a causal relationship between fedratinib and the adverse event.

Causality should be assessed and provided for each AE based on currently available information. Causality is to be reassessed and provided as additional information becomes available.

If an event is assessed as suspected of being related to a comparator, ancillary or additional IP that has not been manufactured or provided by Celgene-Impact, please provide the name of the manufacturer when reporting the event.

10.2.4. Duration

For each AE, the Investigator will provide a record of the start and stop dates of the event.

10.2.5. Action Taken

The Investigator will report the action taken with fedratinib as a result of each AE, as applicable (eg, discontinuation, interruption, or dose reduction of IP, as appropriate) and report if concomitant and/or additional treatments were given for the event.

10.2.6. Outcome

The Investigator will report the outcome of the event for each AE.

All SAEs that have not resolved upon discontinuation of the subject's participation in the study must be followed until recovered (returned to baseline), recovered with sequelae, or death (due to the SAE).

